4.3 Withdrawal Criteria

Participation of a subject in this clinical trial may be discontinued for any of the following reasons:

- Withdrawal of consent or a subject request for discontinuation from the clinical trial for any reason;
- Occurrence of any medical condition or circumstance that exposes the subject to substantial risk and/or does not allow the subject to adhere to the requirements of the protocol;
- Any SAE, clinically significant AE, severe laboratory abnormality, intercurrent illness, or other medical condition which indicates to the Investigator that continued participation is not in the best interest of the subject;
- Pregnancy;
- Requirement of prohibited concomitant medication;
- Subject failure to comply with protocol requirements or clinical trial-related procedures; or
- Termination of the clinical trial by the Sponsor or the regulatory authority.

Unless a subject withdraws consent for further follow-up, subjects who discontinue study drug (ADX-629 or placebo) will continue with the clinical trial for acquisition of safety and efficacy assessments through the Day 60 telephone follow-up visit. If a subject withdraws prematurely from

the clinical trial prior to the EOT visit (Day 28), clinical trial staff should make every effort to complete the full panel of assessments scheduled for the EOT visit (Day 28). The reason for subject withdrawal must be documented in the electronic case report form (eCRF).

Withdrawn subjects will not be replaced.

[figure not shown]

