### 2.2 Study Design

#### 2.2.1 *Overview*

ADX-629-COVID-19-001 is a Phase 2a, randomized, double-blind, placebo-controlled, clinical trial to evaluate the safety, tolerability, efficacy, and PD of ADX-629, administered orally, in adult subjects with COVID-19 of moderate severity. Approximately 30 subjects will be randomized in a 2:1 ratio (ADX-629 to placebo) to receive either ADX-629 300 mg *bis in die* or twice daily (BID) or placebo BID for up to 28 days.

Treatment will begin on Day 1 following randomization. In addition to ADX-629 or placebo, all subjects will receive standard of care treatment for COVID-19. Treatment may commence whether a subject is hospitalized or is treated as an outpatient at Screening. During the Treatment Period (Days 1 to 28/End of Treatment [EOT]), all subjects will receive study drug (either ADX-629 or placebo) BID. The study drug will continue to be taken on an outpatient basis if a subject is discharged from the hospital prior to Day 28 for hospitalized subjects. If a subject is placed on mechanical ventilation and/or is otherwise unable to ingest an oral tablet, dosing will be stopped. However, the subject will continue to be monitored for efficacy and safety. Dosing of the study drug may resume once the subject is able to safely ingest an oral tablet.

All subjects will also have an assessment using the NIAID ordinal scale score daily on Days 1 to 28/EOT. The NIAID score will be evaluated directly for inpatient subjects and assessed via a subject diary for outpatient subjects through Day 28.

After treatment is completed, subjects will undergo a follow-up visit on Day 35 ( $\pm 3$  days) and a telephone follow-up on Day 60 ( $\pm 3$  days). The purpose of the telephone follow-up is to assess survival status and evaluate for COVID-19 relapse. A telephone follow-up visit may be performed in lieu of the Day 35 follow-up visit if the subject is unable to attend in person.

The schedule of study assessments is described in Appendix A.

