#### 2.2.3 *Study Drug*

ADX-629 and the corresponding placebo will each be available as a tablet for oral administration. The study drug will be packaged in a kit with 2 bottles, each bottle containing thirty (30) 300 mg tablets.

ADX-629 and the corresponding placebo will each be administered orally as a tablet, at the discretion of the Investigator, without food, defined as no food for at least 2 hours prior to dosing and at least 1 hour after dosing. Each subject will receive either ADX-629 300 mg BID or placebo BID for up to 28 days. If a subject is temporarily unable to tolerate dosing, a temporary dose interruption of up to 2 days may be permitted, after discussion with the Medical Monitor. No dose reductions will be permitted.

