### 3.3.7 Study Drug Exposure and Compliance

Days of exposure to study drug will be calculated as date of last dose of study drug – date of first dose of study drug + 1. Note that the exposure calculation is intended to describe the length of time a subject was exposed to study drug and therefore does not take study drug interruptions into account. Days of exposure to study drug will be summarized by treatment based on the Safety Population with descriptive statistics and with counts and percentages of subjects with exposure in the following categories:

- <1 week (<7 days)
- 1 - <2 weeks (7 - 13 days)
- 2 - <3 weeks (14 – 20 days)
- 3- <4 weeks (21 – 27 days)
- $\geq$ 4 weeks ( $\geq$ 28 days)

Percent compliance to the study drug regimen will be calculated as  $100 \times$  number of actual tablets taken / number of expected tablets taken. The number of actual tablets taken will be calculated as (# of tablets dispensed - # of tablets returned). The number of tablets expected will be calculated as (date of last visit in Treatment Period [Day 28/EOT] – date of randomization + 1)  $\times$  2, i.e., the number of days study drug was expected to be taken  $\times$  2 tablets per day. Percent compliance to the study drug regimen will be summarized by treatment based on the Safety Population with descriptive statistics and with counts and percentages of subjects with compliance in the following categories:

- <80%
- 80-120%
- >120%

All study drug accountability data and study drug administration (inpatient) data will be listed.

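### The compliance denominator in SAP 3.3.7 counts days of protocol-required dosing stop as missed doses, contrary to its own description, and the numerator counts unreturned tablets as taken

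*SAP*

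**What the plan says.** SAP 3.3.7 defines percent compliance as 100 × tablets taken / tablets expected, summarized by arm in the Safety Population with categories <80%, 80-120% and >120%.

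- **Numerator:** "The number of actual tablets taken will be calculated as (# of tablets dispensed - # of tablets returned". There is no rule for lost or unreturned bottles.
- **Denominator:** ("date of last visit in Treatment Period [Day 28/EOT] – date of randomization + 1") × 2. The same sentence explains this as "the number of days study drug was expected to be taken", times two tablets a day. Nothing is deducted for stopped or held dosing.

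Other sections bear on the formula:

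- **Dosing stops, follow-up continues:** SAP 2.2.1 says "If a subject is placed on mechanical ventilation and/or is otherwise unable to ingest an oral tablet, dosing will be stopped", and monitoring goes on. The stopping criteria in the Protocol synopsis end dosing but keep the subject in follow-up (the criteria themselves are redacted). Protocol 4.3 adds that "subjects who discontinue study drug (ADX-629 or placebo) will continue with the clinical trial".
- **Withdrawal from the trial:** Protocol 6.6 replaces Day 28 with an early termination visit.
- **Supply:** SAP 2.2.3 says "The study drug will be packaged in a kit with 2 bottles, each bottle containing thirty (30) 300 mg tablets". The number of kits per subject is not visible, because Protocol 5.5.2 is redacted.

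**The concern.** On a day when the documents themselves stop dosing, no tablet is due. The calendar formula still expects two. Its result therefore contradicts the SAP's own account of what it measures, and it does so for the sickest subjects and for those taken off drug on safety grounds. Two subjects with the same drug-taking can also score differently only because one stayed in follow-up.

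The numerator has a different weakness. Dispensed minus returned equals taken only if every unused tablet comes back.

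The primary objective is safety and tolerability, and percent compliance is the only planned summary of how many tablets were taken. About 30 subjects are randomized 2:1, so roughly 20 and 10 per arm. One misclassified subject moves a category by about 5 percentage points on ADX-629 and 10 on placebo.

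**Working it through.** The documents give no compliance result to reproduce, so the check applies the SAP formula directly.

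**Inputs**

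- Two tablets a day for up to 28 days (SAP 2.2.3): 28 × 2 = 56 expected.
- Kit size: 2 × 30 = 60 tablets (SAP 2.2.3).
- Randomization on Day 1 (Protocol 6.3.1).
- Assumed: two doses on every dosing day, including the first and last; Day 28 visit on its nominal day.
- Assumed where stated: one kit per subject (range one to two), and the day of stopping (range Day 3 to Day 21).

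**1. Days of required stop, every due tablet taken, the rest returned, followed to Day 28.** Score = (56 − 2 × days stopped) / 56.

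| Days stopped | Score |
|---|---|
| 2 | 52/56 = 92.9% |
| 5 | 46/56 = 82.1% |
| 6 | 44/56 = 78.6% |
| 7 | 42/56 = 75.0% |
| 10 | 36/56 = 64.3% |

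Six or more days put a subject who missed no due dose into the <80% category.

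**2. Required permanent stop, every due tablet taken, the rest returned.** Followed to Day 28, the score is (2 × stop day) / 56. Withdrawn with an early termination visit on the stop day, and that visit taken as the last Treatment Period visit, it is (2 × stop day) / (2 × stop day) = 100%.

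| Stop day | Followed to Day 28 | Withdrawn that day |
|---|---|---|
| 3 | 6/56 = 10.7% | 100% |
| 7 | 14/56 = 25.0% | 100% |
| 10 | 20/56 = 35.7% | 100% |
| 14 | 28/56 = 50.0% | 100% |
| 21 | 42/56 = 75.0% | 100% |

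Steps 1 and 2 do not depend on the number of kits.

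**3. Nothing returned, one kit assumed.**

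- Last visit at Day 28: 60/56 = 107.1%, whether the subject took 20 tablets or 56. This falls in the 80-120% band.
- The same 107.1% results if a subject takes four tablets a day and empties the kit in 60/4 = 15 days.
- Exceeding 120% on 56 expected needs more than 1.2 × 56 = 67.2 tablets, so at least 68. One kit cannot supply them.
- With an earlier last visit: Day 25 gives 60/50 = 120.0%, not above the limit; Day 24 gives 60/48 = 125%; Day 14 gives 60/28 = 214%. Early leavers who return nothing do land in >120%, but because of missing bottles.

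**4. Two kits instead.** The Day 28 maximum becomes 120/56 = 214%, so >120% is reachable.

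**The case against.** The case for leaving the plan alone has real substance.

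- **No analysis uses the percentage.** The table is descriptive, the Per-Protocol definition in SAP 3.2.2 states no compliance cut-off, and all efficacy assessments are exploratory. This stands and limits the importance of the point.
- **Other outputs cover part of the ground.** SAP 3.3.1 summarizes discontinuation of treatment and of study by arm, with reasons. SAP 3.3.7 summarizes exposure days and lists accountability and inpatient administration data. An arm difference in discontinuation would be visible. None of these corrects the percentage, however, and the exposure calculation by its own terms ignores interruptions.
- **A low score can be right.** For a subject who chooses to stop, 20 of 56 planned tablets is a fair measure of adherence. This stands, so only stops and holds under the protocol should be deducted.
- **Short holds matter little.** The permitted interruption of up to 2 days costs about 7 points and stays within 80-120%.

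A reader might infer more: that the >120% category can never detect overdosing in completers. The documents do not support that. They describe how a kit is packed, not how many are dispensed, and with two kits the category is reachable. Nor is 36% against 100% a fixed property of the formula. It follows from an illustrative Day 10 stop.

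**Conclusion.** The denominator is wrong as written. It contradicts the SAP's own description for a group that the documents plainly foresee: subjects whose dosing is stopped under the protocol while follow-up continues. Six or more such days move an otherwise fully compliant subject below 80%. A required permanent stop scores between 11% (Day 3) and 75% (Day 21) if the subject is followed to Day 28, against 100% if the subject is withdrawn that day.

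The numerator also treats unreturned tablets as taken. That follows from the text, but the 107% figure and the Day 28 ceiling below 120% hold only under one kit per subject.

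This is a small defect: it affects a descriptive table behind the primary safety objective, and no planned inference depends on it.

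**What to change.** Amend SAP 3.3.7 before database lock:

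- Define expected tablets as 2 × (calendar days from randomization to last Treatment Period visit − days on which dosing was stopped or held under the protocol). The Day 10 required stop then scores 20/20 = 100% under either follow-up status.
- Keep days after subject-initiated stopping in the denominator. A first-to-last-dose denominator is not a good substitute, because it would score a subject who simply quits at Day 10 as 100%.
- Take tablets given on inpatient days from the administration records already collected, and use dispensed minus returned for outpatient days.
- Flag subjects with unreturned bottles and add a sensitivity summary without them. Setting them to missing in the main table would discard data in a trial of about 30.

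Discontinuation needs no new table, since SAP 3.3.1 already covers it; the compliance table should refer to it. Subjects who leave the trial by choice will still have a denominator that ends at their last visit, so the two tables should be read together.

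The cost is SAP wording, minor programming and a coded reason for each stopped or held period. No clinical procedure changes.

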## 3.4 Efficacy Assessment

Efficacy data (i.e., secondary endpoints) will be analyzed by randomized treatment based on the ITT Population. The key efficacy endpoint will also be analyzed based on the PP Population. The trial is exploratory and not formally powered. All assessments will be deemed exploratory.

### 3.4.1 Key Efficacy Endpoint

The key efficacy endpoint is the NIAID ordinal scale score (Table 1) over Day 1 through Day 28.

**Table 1. NIAID 8 Point Ordinal Scale for COVID 19**

Numerical Score	Definition
1	Death

2	Hospitalized, on invasive mechanical ventilation or extracorporeal membrane oxygenation
3	Hospitalized, on noninvasive ventilation or high-flow oxygen devices
4	Hospitalized, requiring supplemental oxygen
5	Hospitalized, not requiring supplemental oxygen – requiring ongoing medical care (COVID-19 related or otherwise)
6	Hospitalized, not requiring supplemental oxygen – no longer requires ongoing medical care
7	Not hospitalized, limitation on activities and/or requiring home oxygen
8	Not hospitalized, no limitation on activities

NIAID scores change from baseline to Day 28 will be summarized by treatment group (ADX-629 or placebo) using descriptive statistics (n, mean, standard deviation, median, minimum, and maximum).

All NIAID data will be listed.

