9.2 Statistical Methods

9.2.1 Analysis of Endpoints

Clinical parameters will be assessed via linear models with repeated measures over 28 days. Sensitivity analyses will be performed using other techniques. The specific statistical analysis methods are detailed in the Statistical Analysis Plan.

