### 3.4.2 Other Efficacy Endpoints

Additional efficacy endpoints include the following:

- Proportion of subjects alive and not mechanically ventilated over Day 1 through Day 28;
- Time to recovery (for hospitalized subjects at Screening), defined as the first day on which the subject has an NIAID score of 6 or larger;
- Time to recovery (for non-hospitalized subjects at Screening), defined as the second consecutive day on which the subject has an improvement in the NIAID ordinal scale by 1 point;
- Proportion of subjects alive and not in the intensive care unit over Day 1 through Day 28;
- Proportion of subjects alive and not in the hospital over Day 1 through Day 28;

- Proportion of subjects alive and not on supplemental oxygen over Day 1 through Day 28;
- Mortality; and
- Time to hospital discharge (for hospitalized subjects), defined as time from first hospital admission to first hospital discharge in the 28 day study period.

The proportions will be presented by treatment group (ADX-629 or placebo). The difference between treatment groups will be analyzed by a Generalized Estimating Equation (GEE) model similar to the MMRM model for the key efficacy endpoint if applicable. If the GEE model does not converge, then the Fisher's exact test will be used.

Time to recovery (censored at Day 28) from randomization and time to hospital discharge will be addressed by Kaplan-Meier analysis, including a comparison between the treatment groups by a log-rank test if applicable.

The mortality rate, calculated as the number of subjects who died by Day 28 divided by the number of subjects randomized, will be summarized by treatment group. The difference between treatment groups will be analyzed by Fisher's exact test if applicable.

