### **3.5 Pharmacodynamic (PD) Assessment**

The PD endpoints include the following:

- RASP plasma concentrations; and
- Plasma exploratory biomarker concentrations (e.g., interleukin [IL]-1 $\beta$ , IL-6, IL-10, and tumor necrosis factor alpha).

For each PD parameter, descriptive statistics (n, mean, standard deviation, median, minimum, maximum) will be summarized by treatment group for the PD Population at pre-dose and post-dose of each scheduled visit.

A MMRM analysis similar to that of the key efficacy endpoints will be used for the analysis of PD endpoints as appropriate.

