## **6 CHANGES FROM PROTOCOL-SPECIFIED STATISTICAL ANALYSES**

[figure not shown]
Laboratory assessments will be summarized by incidence of abnormalities instead of change from baseline values at each visit.

[figure not shown]

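### The key NIAID endpoint spans Days 1 to 28, but SAP 3.4.1 plans only a descriptive Day-28 change, and the MMRM cited in SAP 3.4.2 and 3.5 is not specified in the visible SAP

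*SAP*

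**What the plan says.** **Endpoint.** SAP 3.4.1 states: "The key efficacy endpoint is the NIAID ordinal scale score (Table 1) over Day 1 through Day 28". Protocol 7.2 defines its key secondary endpoint the same way, and both documents have the score taken daily.

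**Analysis in the SAP.** Under Table 1 of SAP 3.4.1, "NIAID scores change from baseline to Day 28 will be summarized by treatment group (ADX-629 or placebo) using descriptive statistics". The only other output there is a listing of the NIAID data.

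**Analysis in the protocol.** Protocol 9.2.1 says: "Clinical parameters will be assessed via linear models with repeated measures over 28 days". It adds sensitivity analyses by unnamed techniques and then hands over: "The specific statistical analysis methods are detailed in the Statistical Analysis Plan". It does not name the NIAID score separately.

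**References to a model.** SAP 3.4.2 analyses the proportions by a GEE model "similar to the MMRM model for the key efficacy endpoint if applicable", with Fisher's exact test as the fallback "If the GEE model does not converge". SAP 3.5 says: "A MMRM analysis similar to that of the key efficacy endpoints will be used for the analysis of PD endpoints as appropriate". Otherwise MMRM appears only in the list of abbreviations, as does compound symmetry, which the body of the SAP never uses.

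**Declared changes.** The only change visible in SAP section 6 is: "Laboratory assessments will be summarized by incidence of abnormalities instead of change from baseline values at each visit".

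**The concern.** There are two gaps. First, a 28-day endpoint is reduced to the change at one day, described arm by arm. The protocol method is neither carried out in the visible SAP nor recorded there as dropped. Second, the GEE and PD analyses are modelled on a parent analysis whose response, terms, days, covariance structure and contrast are not given. A programmer could not build them from the visible text.

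The choice of summary matters because of the ceiling. Protocol 4.2 excludes scores below 5 and the scale ends at 8, so the visible criteria admit baselines 5 to 8, with largest possible gains of +3, +2, +1 and 0. No stratified randomization is described. An unadjusted change score therefore carries chance differences in baseline straight into the arm comparison. SAP 3.3.4 tabulates inpatient status, which separates scores 5 and 6 from 7 and 8. It does not list the baseline NIAID score, so an imbalance between 7 and 8 would not show in that table.

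At stake is the precision and reproducibility of the trial's main efficacy description. The primary safety objective does not depend on it.

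**Working it through.** The plan has no figure to reproduce: it states no alpha, power, effect size or SD. The textual part rests on the sections set out above. The size is an illustration, because no document gives the baseline mix.

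**1. Hand check of imbalance alone (deliberately stylised).** Assume 30 subjects split 20 and 10 without stratification, K inpatients with baseline 5, the rest with baseline 7, everyone at 8 on Day 28, and no drug effect. The mean change in an arm is 1 + 2 × (inpatient proportion), so the arm difference is twice the difference in inpatient proportions.

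- SD = 2 × √[(30/29) × p(1 − p) × (1/20 + 1/10)], with p = K/30.
- For K = 9: p = 0.3, (30/29) × 0.21 × 0.15 = 0.0326, square root 0.1805, doubled 0.361.
- The exact hypergeometric chance that the arms differ by at least 0.5 points is 3% for K = 3, 14% for K = 6, 20% for K = 9, 24% for K = 12 and 25% for K = 15.

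Everyone reaches the ceiling here, so the whole difference is baseline imbalance.

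**2. Less stylised null simulation.** Assumed inputs:

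- 20 versus 10 subjects and 20,000 trials;
- baselines 5/6/7/8 at 20/10/60/10%;
- one-point daily steps up with a median of 6 days per step (daily chance 1 − 0.5^(1/6) = 0.109);
- a 1% daily chance of a one-point fall;
- no deaths, no missing days and no drug effect.

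About 78% are at score 8 on Day 28.

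| Arm difference in | SD |
|---|---|
| Day-28 change, unadjusted | 0.35 |
| Day-28 change, adjusted for baseline | about 0.25 |
| Mean score Days 2–28, unadjusted | 0.30 |
| Mean score Days 2–28, adjusted for baseline | 0.20 |

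The unadjusted Day-28 difference is 0.5 or more in either direction in 17% of trials. This counts differences of exactly 0.5; excluding them gives 13%. The step from 0.35 to 0.20 combines two changes. Baseline adjustment alone gives 0.35 to about 0.25, roughly halving the variance: (0.35/0.25)² = 1.96. Averaging over the post-baseline days gives the rest: (0.25/0.20)² = 1.56.

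**3. Limit of the linear model.** Under the null, the 95% CI for the adjusted mean (t, 27 df) covers about 95%. With an assumed drug effect (median 3 versus 6 days per step), coverage falls to about 0.91, because the spread differs between arms near the ceiling.

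**4. Timing.** Two subjects start at 7. One is at 8 from Day 5, the other from Day 25. Both have a Day-28 change of +1. Their Day 2–28 means are 7 + 24/27 = 7.89 and 7 + 4/27 = 7.15.

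**5. Covariance.** An unstructured matrix for 27 post-baseline days has 27 × 28 / 2 = 378 parameters, too many for 30 subjects. Compound symmetry has 2.

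**The case against.** **Text may be missing.** Two references to an MMRM and an unused compound-symmetry abbreviation would fit a model paragraph that was lost. Figure placeholders surround section 6, and detailed programming specifications are kept in a separate document. Nothing marks a gap in 3.4.1, so loss is unproven, but the point can be made only about the visible SAP. A reader might infer that the sponsor abandoned the model or never prespecified one. The documents show neither.

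**It is exploratory.** SAP 3.4 says so for every assessment, the trial is not powered, and safety is primary. This stands and limits the consequence. It does not explain why lesser endpoints get GEE, log-rank or Fisher comparisons while the key endpoint gets none.

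**Other outputs help.** Time to recovery is compared by log-rank test, with separate definitions by hospitalization at Screening, so the timing of recovery is already captured in part; it would separate the two subjects in step 4. A reader could also form an unadjusted difference from n, mean and SD. The proportions keep a Fisher fallback and PD keeps its descriptive summaries. None of these gives a baseline-adjusted NIAID estimate.

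**The baseline range is uncertain.** Inclusion criterion 5 and several exclusion criteria are redacted and could narrow the range 5 to 8. The figures are therefore illustrations.

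**Day 28 may mean each day up to Day 28.** That reading would still be descriptive and would still leave the MMRM undefined.

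**Conclusion.** The point holds for the visible text and should be fixed. The key endpoint is longitudinal, its stated analysis is a descriptive single-day change, the protocol's repeated-measures analysis is neither specified nor declared dropped, and two other analyses refer to an undefined model.

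Under the assumed mix of baselines, the unadjusted Day-28 difference has SD 0.35 and a 17% chance of reaching 0.5 points with no drug effect. The SD is about 0.25 with baseline adjustment and 0.20 with adjustment and averaging. These figures assume complete data, no deaths and the full 5 to 8 baseline range.

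A reader might infer that the unadjusted comparison is biased, or that the trial's conclusion is at risk. Neither follows. Randomization makes a chance imbalance equally likely in either direction on average, so the cost is precision and interpretability in one small trial. The primary safety conclusion is unaffected.

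**What to change.** In SAP 3.4.1:

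- Specify a repeated-measures model on the post-baseline daily NIAID scores with treatment, day, treatment-by-day and baseline NIAID score. Use a covariance structure that 30 subjects can support, for example compound symmetry.
- Report the adjusted treatment difference, for example averaged over the post-baseline days, with a 95% CI on between-subject degrees of freedom.
- State how days after death and missed diary days are handled.
- Keep the Day-28 change as a supporting description.
- Add one sensitivity analysis, as protocol 9.2.1 promises, for example an ordinal model or one allowing unequal variances. The coverage of about 0.91 in step 3 is the reason.

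Elsewhere in the SAP:

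- Add baseline NIAID score to the 3.3.4 table.
- Point the 3.4.2 GEE and the 3.5 PD analysis to this model. For PD, take the Day 1 pre-dose sample as baseline and the post-dose samples as responses.

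If the sponsor means to drop the model, record that in section 6 and define the GEE and PD models on their own. If the model is already written elsewhere, bring it into the SAP.

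Make the change before unblinding, so that the model is not chosen with the results in view. The cost is SAP wording, one model, one sensitivity analysis and one table row on data already collected, with no added subjects or procedures. The downside is a little more analysis work.
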